### Study Arm 1: Tele-HCV Treatment Arm Procedures:

Participants allocated to telemedicine intervention arm are scheduled for treatment assessment by a study clinician. For a majority of participants, this will also be the treatment initiation visit. If additional studies are necessary for routine treatment decision making, peers will assist participants in navigating health system barriers and arrangement of second telemedicine visit. The telemedicine study clinician will perform a standard of care hepatitis C treatment initiation history and submit a prescription for DAAs. Prior authorizations will be completed by study clinician pharmacist.

All patients initiating treatment will be prescribed HCV medication treatment for 4 weeks at a time. The majority of patients will require two separate dispensations at week 0 and week 4 for a total of 8 weeks of medications, with a small subset requiring third, 4-week dispensation for a total of 12 weeks of therapy. The study clinical pharmacist will check in with the participant by telephone or telemedicine visit at week 0, week 4, and end of treatment to 1) determine general medication tolerance, 2) assess quality of adherence and 3) dispense medications by mail or ensure medications received, depending on participant's insurance. Peers will assist participants in keeping telehealth appointments and navigating medication pick up or storage, if not mailed directly to the home. Participants who report new onset of jaundice or other signs of hepatic decompensation during participation will be scheduled for a follow up telemedicine visit with a physician by the research assistant, receive repeat laboratory studies if needed, and if necessary, be referred to local providers for ongoing medical care. If problems or side effects arise during treatment, participants will call the research assistant, who will connect them to a study clinician.

HCV labs will be repeated at 12 weeks post end of treatment and results will be relayed to the participant in the SVR12 follow up visit with the research assistant, along with follow up surveys. Those successfully achieving SVR12 will be counseled on ongoing harm reduction methods. Those showing persistent HCV viremia at 12 weeks post treatment will be referred to community-based HCV treatment providers for treatment re-initiation. All will be scheduled for 36 week post end of treatment survey visit.

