#### Study Arm 2: Community Linkage-To Care Arm (Control Condition) Procedures:

Participants allocated to the community linkage-to-care arm will complete screening, be offered enrollment, and undergo informed consent as in the telemedicine arm. Following study inclusion and enrollment, research staff will refer the participant to a local community health clinic to engage in hepatitis C care and seek treatment. Peers will assist patients to engage with local primary care and health plan resources and will receive an information sheet on optional clinics to attend and questions to ask their provider. TAU participants will be encouraged to take this to their visit. Research assistants will outreach to participants regularly to determine if they have engaged in local health resources and schedule assessment visits. A bidirectional release of information will be requested. The study clinical pharmacist or research assistant will assess adherence medication adherence at week 4 and end of treatment via telephone. SVR12 laboratory testing will be performed by the community provider with at least one telephone reminder prior to lab due date. 12 weeks post end of treatment study assessments will coincide with SVR12 lab results visit and 36 week post end of treatment assessments performed as in the telemedicine arm.

Chart abstraction for participants in both arms will be performed in order to assess the number of and types of interactions the peers have with participants.

In either arm, participants who do not initiate treatment by 12 weeks after randomization will begin their assessment timeline, mirroring treatment timeline for an 8-week direct acting antiviral regimen. For these participants, the study research assistant will collect study assessments at week 16 (corresponding to 4-week post-treatment initiation), week 20-22 (corresponding to end of treatment visit), week 32 (corresponding to 12 weeks post-treatment visit), and week 56 (corresponding to 36

weeks post-treatment visit) after randomization; the primary study outcome will be assessed at 32 weeks after randomization.

Participant Assessments:

Phase 1:

- Blood draw and DBS specimen collection for HCV RNA and Hepatitis B core antibody

Phase 2:

Assessment/Activity	Pre-Screen	Screen	Baseline (Week 0)	4-Week after treatment initiation	End of Treatment	12-week Post-Treatment	***36-Week Post Treatment Completion	As Needed

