## Data Analysis:

Pre-specified analyses for this study will be intention-to-treat (ITT) comparisons between telemedicine and treatment as usual (local treatment referral) on primary and secondary outcomes. Prior to conducting these analyses, we will compare baseline covariate distributions (demographics, etc.) between randomized groups using standardized mean differences (SMDs) and bivariate statistical tests (e.g. t-tests, Chi-square tests). If a significant imbalance in any variable is noted, i.e., a SMD > 0.25 and  $p < .2$ , we will include that variable as a covariate in future analyses. All primary and secondary analyses will utilize generalized linear (mixed) models (GLMMs) with distributions and link functions appropriate for the distribution of the outcome variable. Fixed effects of interest in the models will be timepoint (baseline, 4 weeks, end of treatment, 12 weeks post-treatment, 36 weeks post-treatment), randomized group (telemedicine vs. TAU), and their interaction. If more than one timepoint is included in the analysis, GLMMs will include person-level random intercepts to account for repeated measurements on subjects. Hypotheses will be tested using between-group comparisons at each timepoint of interest, or within-group comparisons across timepoints.

Hypothesis 1: Participants randomized to receive tele-HCV treatment will have superior SVR-12 rates compared to those randomized to TAU (referral for local treatment).

Analytic strategy: We assess the effect of telemedicine versus TAU on SVR at 12 weeks post-treatment completion using logistic regression. Missing HCV viral load data will be considered non-suppressed in the main ITT analysis. Sensitivity analyses will include a per-protocol analysis and a repeat of the main analysis using multiple imputation of missing data.

Hypothesis 2: Participants randomized to receive tele-HCV treatment will have superior rates of HCV treatment initiation (filled first prescription) compared to those randomized to TAU.

Analytic strategy: We assess the effect of telemedicine versus TAU on treatment initiation by 4 weeks post-baseline using logistic regression. Missing treatment initiation data will be considered non-initiated in the main ITT analysis. Sensitivity analyses will include a per-protocol analysis and a repeat of the main analysis using multiple imputation of missing data.

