Hypothesis 3: Participants randomized to receive tele-HCV treatment will have superior rates of HCV treatment completion (filled final prescription and self-reported > 90% HCV treatment pills taken) compared to those randomized to TAU.

Analytic strategy: We assess the effect of telemedicine versus TAU on treatment completion by 12 weeks post-baseline using logistic regression. Missing treatment completion data will be considered incomplete in the main ITT analysis. Sensitivity analyses will include a per-protocol analysis and a repeat of the main analysis using multiple imputation of missing data.

Hypothesis 4: Participants randomized to receive tele-HCV treatment will have a higher likelihood of engagement with harm reduction resources, lower rates of substance use, lower stigma, and higher engagement in addiction treatment resources compared to those randomized to TAU (referral for local treatment).

Analytic strategy: We assess the effect of telemedicine versus TAU on these outcomes at all post-baseline timepoints using mixed effects regression models. Missing outcome data will be handled using full information maximum likelihood. We will conduct per-protocol analyses as sensitivity analyses.

**Qualitative Evaluation.** Audio-recorded interviews will be professionally transcribed; transcripts will be uploaded into qualitative analysis software (NVivo™). Comagine research staff create a coding scheme, conduct coding, and revise in an iterative process that has been successfully implemented by the study team in other mixed-methods projects. The qualitative data provides complementary information to illuminate and expand quantitative findings, including survey results and measures of treatment initiation and completion.

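### The per-protocol sensitivity analyses of SVR12, treatment initiation and treatment completion have no defined population, and the usual definitions would condition on uptake of care, which is the effect under test

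*Combined protocol and SAP*

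**What the plan says.** The Data Analysis section makes intention-to-treat the main analysis: "Pre-specified analyses for this study will be intention-to-treat (ITT) comparisons between telemedicine and treatment as usual (local treatment referral) on primary and secondary outcomes". Under Hypotheses 1 (SVR12), 2 (initiation) and 3 (completion) it adds: "Sensitivity analyses will include a per-protocol analysis", alongside a rerun of the main analysis with multiple imputation. Under Hypothesis 4 (harm reduction, substance use, stigma, addiction treatment) it says: "We will conduct per-protocol analyses as sensitivity analyses". No section defines the per-protocol population for either arm.

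The two arms are assigned different first steps:

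- **Telemedicine** (Study Arm 1 procedures): "Participants allocated to telemedicine intervention arm are scheduled for treatment assessment by a study clinician". Of that visit the protocol says: "For a majority of participants, this will also be the treatment initiation visit".
- **Control** (Study Arm 2 procedures): "research staff will refer the participant to a local community health clinic to engage in hepatitis C care and seek treatment".

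Initiation is defined as a filled first prescription (Hypothesis 2). Completion is a filled final prescription plus more than 90% of pills taken by self-report (Hypothesis 3). Under Study Measures, anyone who has not started within 6 months counts as an SVR12 failure.

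**The concern.** In a drug trial, a per-protocol set asks what happens among people who took the drug as intended. Here the randomized intervention is a route into treatment, so whether people take that route is the result. Removing those who did not take it removes the failures that the strategy is meant to prevent.

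The arms are also unequal in what receiving the strategy requires. A telemedicine participant has to attend a visit, whereas a control participant only has to be given a referral, which staff can do for everyone. Applied literally, such a rule excludes non-attenders from one arm only, and those non-attenders have almost no route to a filled prescription through the study.

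An analysis presented as a robustness check could therefore seem to confirm or contradict the primary result through selection alone. Because the trial is non-blinded and the set is undefined, the rule could also be chosen after outcomes are known.

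**Working it through.** The plan gives no figure to reproduce: it has no event rates, allocation ratio, power or per-protocol size for Phase 2. The only document input is the target of up to 200 participants (Number of Subjects). Everything else here is assumed: 100 per arm, a two-sided 5% test (2.5% in favour of telemedicine), and the rates shown.

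**1. Telemedicine attenders vs all referred controls, arms truly equal.** Let *p* be the initiation rate in both arms and *a* the share of the telemedicine arm attending the visit, with all its starters among the attenders. The per-protocol rates are *p/a* vs *p*. With *p* = 30%:

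| Attendance *a* | Per-protocol rates | Falsely favours telemedicine |
|---|---|---|
| 50% | 60.0% vs 30% | 94.5% |
| 60% | 50.0% vs 30% | 71.6% |
| 70% | 42.9% vs 30% | 41.1% |
| 80% | 37.5% vs 30% | 18.7% |
| 90% | 33.3% vs 30% | 7.3% |

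These come from 100,000 simulated trials per row with a pooled two-proportion z-test. ITT on the same data gave 2.5% to 2.6%.

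Formula check at *a* = 60% (60 vs 100 people):
- Pooled rate: 60/160 = 0.375.
- Null standard error: √[0.375 × 0.625 × (1/60 + 1/100)] = 0.0791.
- Alternative standard error: √[0.25/60 + 0.21/100] = 0.0792.
- Probability: Φ[(0.20 − 1.96 × 0.0791)/0.0792] = Φ(0.57) ≈ 0.715.

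Over *p* from 10% to 60% and *a* from 50% to 90%, the false-finding rate runs from 4% to about 100%. At 90% attendance it stays between 4% and 16%.

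**2. SVR12 under the same rule.** Assume 95% of starters are cured. With *p* = 30% and *a* = 60%, SVR12 is 0.95 × 50% = 47.5% vs 0.95 × 30% = 28.5%, and the false-finding rate is 68%. At *a* = 80% it is 18%.

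**3. Visit attendance required in both arms.**
- Equal initiation (30%), attendance 80% telemedicine vs 60% control: 30/80 = 37.5% vs 30/60 = 50%. The bias now runs against telemedicine, with 32% of trials significantly favouring control and 0.03% favouring telemedicine.
- Real benefit acting through attendance (80% vs 40%), with 80% of attenders starting in each arm: ITT is 0.8 × 0.8 = 64% vs 0.8 × 0.4 = 32%, which is detected 99.7% of the time. Per-protocol is 80% vs 80% and favours telemedicine 2.8% of the time.

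**4. Set restricted to people who started or adhered.** Initiation becomes 100% in both arms by construction. Adherence overlaps the completion outcome. For SVR12, with 95% cure among starters, ITT of 0.95 × 64% = 60.8% vs 0.95 × 32% = 30.4% becomes 95% vs 95%.

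**5. Set that does not depend on uptake.** Excluding 5% at random in each arm, with 30% initiation, gives 2.4% false findings for telemedicine, which is close to nominal.

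**The case against.** The strongest reply is that the plan never says visit attendance defines the set. What is written is an undefined population, and a set based on confirmed eligibility is also commonly called per-protocol and would not carry this bias. That stands, and step 5 bears it out. The point is therefore conditional on the rule chosen.

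Other parts of the reply also stand:

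- The visit is not the outcome. It is the initiation visit for most participants rather than all, and the outcome is a filled prescription.
- The control arm involves more than a referral. Peers help participants engage with local care, and staff follow up regularly, so a rule requiring engagement in both arms is possible. Step 3 shows that this changes the direction of the bias without removing it.
- Attendance may be high. Participants must be seeking treatment, and peers help them keep telehealth appointments. At 90% attendance the inflation is modest.
- Main conclusions rest on ITT, and Hypotheses 1 to 3 also have a multiple-imputation sensitivity analysis.

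The reply does not make the point a mere missing detail. For initiation and completion, the ordinary meanings of per-protocol are steps towards the outcome or overlap it, so writing one of them down would not make the analysis informative.

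**Conclusion.** The point holds in conditional form. Per-protocol analyses are planned for three uptake-dependent outcomes with no stated population, and the usual definitions would condition on post-randomization uptake. Under equal arms, 100 per arm and 30% initiation (all assumed), an attended-versus-referred rule falsely favours telemedicine in roughly 7% to 95% of trials as attendance falls from 90% to 50%. A two-sided visit rule can reverse the bias or erase a real effect.

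A reader might infer more than this, and the documents do not support it:

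- *That the analysis selects on the outcome itself and would confirm telemedicine whatever the truth.* No such rule is written, and both size and direction depend on the rule and on attendance rates that the plan does not give.
- *That every per-protocol set is biased.* One fixed by pre-randomization facts is not.
- *That Hypothesis 4 is biased in the same way.* A per-protocol analysis is the only sensitivity analysis listed there, but no bias has been shown for those outcomes.
- *That the main result is at risk.* The ITT analyses are unaffected; only the support drawn from the sensitivity analyses is in question.

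**What to change.** Amend the four hypothesis paragraphs in Data Analysis before outcome data are examined:

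- **Hypotheses 2 and 3:** delete the per-protocol analysis and keep multiple imputation.
- **Hypothesis 1, and Hypothesis 4 for consistency:** restrict any such set to criteria fixed before randomization, for example eligibility confirmed from screening data, applied identically in both arms.
- **SVR12 among starters:** report by arm as description, without a between-arm test.
- **Effect of receiving telemedicine, if wanted:** use a complier-average (instrumental-variable) estimate with randomized arm as instrument. State its assumptions, chiefly that assignment affects the outcome only through receiving the telemedicine visit. If controls have no access to that visit, the estimate is the ITT difference divided by attendance. In the equal-arms example this gives (30% − 30%)/0.60 = 0, as it should.

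The cost is wording only, with no new data. One familiar analysis is lost. Because eligibility is screened before enrollment, the replacement set may lie close to ITT and add little.

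### Counting unknown treatment initiation as non-initiation leaves Hypothesis 2 (and, more weakly, the final-fill part of Hypothesis 3) open to differential ascertainment that would probably favour telemedicine

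*Combined protocol and SAP*

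**What the plan says.** The Data Analysis section defines Hypothesis 2 as "superior rates of HCV treatment initiation (filled first prescription) compared to those randomized to TAU" and gives the window and model: "We assess the effect of telemedicine versus TAU on treatment initiation by 4 weeks post-baseline using logistic regression". The rule for missing values is "Missing treatment initiation data will be considered non-initiated in the main ITT analysis". Hypothesis 3 requires "filled final prescription and self-reported > 90% HCV treatment pills taken", with a parallel rule: "Missing treatment completion data will be considered incomplete in the main ITT analysis". For both hypotheses a per-protocol analysis and a repeat with multiple imputation are planned as sensitivity analyses.

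The two arms learn of fills by different routes.

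- **Telemedicine (Study Arm 1 procedures).** The study clinician is to "submit a prescription for DAAs. Prior authorizations will be completed by study clinician pharmacist". At week 0, week 4 and end of treatment the study pharmacist is to "dispense medications by mail or ensure medications received", depending on the participant's insurance.
- **Control (Study Arm 2 procedures).** A local provider prescribes. "Research assistants will outreach to participants regularly to determine if they have engaged in local health resources". A two-way release of information is requested, and adherence is assessed by telephone at week 4 and end of treatment.

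Chart abstraction covers both arms, but its stated purpose is to describe peer interactions. The assessment schedule adds visits to HCV treatment providers and has no item for pharmacy fills or insurer claims.

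**The concern.** Scoring missing as failure is usually defended as conservative. That defence needs unknown status to be about equally common, and about equally likely to hide a success, in both arms. Here a telemedicine fill is generated and followed up within study care. A control fill happens outside the study and has to be discovered. Each one not discovered is scored as a failure, so part of any observed difference could reflect who was watching rather than who started treatment.

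Timing adds to this. Hypothesis 2 is judged at 4 weeks after baseline, but the first follow-up assessment is timed from treatment start, or falls at week 16 for those not started by week 12. No scheduled assessment in control matches the endpoint window.

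At stake is a superiority claim on treatment initiation, a secondary outcome. The point does not concern the primary SVR12 analysis.

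**Working it through.** **No figure to reproduce.** The documents give no Phase 2 power calculation, expected initiation rate, missing-data rate or allocation ratio. They give only a recruitment ceiling of 200. Everything below is illustration under stated assumptions.

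**Assumptions.** 1:1 allocation, so 100 per arm. No true difference. Pooled two-proportion z test at 1.96, which is the score test of the unadjusted logistic model. Binomial outcomes enumerated exactly. Results are the probability of a significant result in favour of telemedicine, nominally 2.5%.

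**Formula.** Let m be the share with unknown status and q the share of those unknowns who truly initiated, with T for telemedicine and C for control. Under the rule:

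- observed rate = true rate − m × q
- bias in the risk difference (telemedicine − control) = mC × qC − mT × qT

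**Base case.** True rate 60% in both arms, mT = 2%, qT = 60%. Telemedicine observed = 0.60 − 0.02 × 0.60 = 58.8%. With mC = 2% and qC = 60% as well, the arms match and the false-positive rate is 2.6%.

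| Control unknown (mC) | qC = 60%: observed control, false positive | qC = 20%: observed control, false positive | qC = 0%: observed control, false positive |
|---|---|---|---|
| 10% | 54.0%, 10.7% | 58.0%, 3.4% | 60.0%, 1.7% |
| 15% | 51.0%, 20.8% | 57.0%, 4.7% | 60.0%, 1.7% |
| 25% | 45.0%, 51.8% | 55.0%, 8.3% | 60.0%, 1.7% |

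**Where the direction turns.** The bias favours telemedicine when qC exceeds mT × qT / mC = 0.012 / mC. That is 12% at mC = 10%, 8% at 15% and 4.8% at 25%. If fewer control unknowns than this had started, the bias runs slightly against telemedicine.

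**Other inputs** (unknowns initiate at the true rate in each arm):

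- True rate 20%, mT = 2%: telemedicine observed 19.6%; control 18.0%, 17.0% and 15.0% at mC = 10%, 15% and 25%; false positives 4.9%, 7.0% and 13.7%.
- True rate 10%, mT = 2%: 4.0%, 5.2% and 8.5%.
- True rate 60%, mT = 5%, mC = 10%: observed 57.0% versus 54.0%; false positive 6.7%.

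**What multiple imputation does.** Without informative covariates its large-sample estimate is the rate among participants with known status. When unknowns initiate like everyone else, that equals the true 60% in both arms and the problem is repaired. When qC = 20%, the control estimate is 0.58/0.90 = 64.4%, 0.57/0.85 = 67.1% or 0.55/0.75 = 73.3% at mC = 10%, 15% or 25%, all too high. It can also miss in the other direction. With a true control rate of 50%, 20% of initiators unknown and no non-initiators unknown, it gives 0.40/(0.40 + 0.50) = 44.4%, against 40% under the main rule.

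**The case against.** The strongest case on the other side has four parts.

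1. **Bias is not demonstrated.** A reader might infer that the rule is known to bias Hypothesis 2 toward telemedicine. The documents do not support that. They give no missing-data rates, and control participants whom nobody can reach may mostly not have started, in which case the rule is close to correct. This stands, and it limits the point to exposure with a probable direction. Two features make zero unseen control fills an unsafe assumption: participants must be insured and seeking treatment to enter, and peers help control participants reach local care.

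2. **Multiple imputation is already planned, and it repairs the very scenario that yields 52%.** This stands for that scenario. It does not settle the matter: imputation is only a sensitivity analysis, and it misses when missingness depends on initiation.

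3. **The asymmetry is partial.** Control has regular outreach, a release, telephone adherence contacts, chart abstraction of provider visits, treatment surveys not restricted to telemedicine, and a 12-week rule in either arm that requires initiation status to be tracked. In telemedicine, where the study does not mail the drug, confirming receipt also depends on reaching the participant. This stands and argues for smaller gaps, such as 5% versus 10%. But most of the control safeguards depend on contact or consent, and none is a record of fills.

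4. **Hypothesis 3 does not follow directly.** A reader might carry the argument over at full strength. Completion also needs self-reported pill-taking, obtained by contact in both arms, so a fill seen by the study cannot by itself establish completion. Only the final-fill component shares the asymmetry.

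**Conclusion.** The point holds as one of exposure. The main analysis of Hypothesis 2, and more weakly the final-fill component of Hypothesis 3, combines a missing-equals-failure rule with ascertainment that differs by arm by design. The probable direction favours telemedicine, so the rule should not be presented as conservative.

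The size cannot be fixed from the documents. Under the assumed 100 per arm, 60% true initiation and 2% unknown in telemedicine, the one-sided false-positive rate for 10% to 25% unknown in control ranges from about 2% (no control unknowns started) through 3% to 8% (20% started) to 11% to 52% (unknowns like everyone else). A true rate of 20% brings the last range down to 5% to 14%. The 52% figure is the top of this range and not an expected value.

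**What to change.** 1. Seek first-fill and final-fill status from the same source in both arms: pharmacy or insurer dispensing records, under a release requested from every participant. Insurance enrolment is already an inclusion criterion, and a release is already planned in control. Code a participant as non-initiated only after that search.
2. Report the number with unknown status by arm, for initiation and for final fill.
3. Add to the analysis plan, for Hypothesis 2 and the fill component of Hypothesis 3, a tipping-point analysis that varies initiation (or final fill) among unknowns separately by arm. State in advance that a superiority claim on initiation will be qualified if it tips under plausible values.

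The cost is a release extended to both arms, some record requests and a small added analysis. Items 2 and 3 need only wording in the analysis plan. If ascertainment is equal in both arms, the bias under no true effect is zero and the false-positive rate returns to its nominal level.
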